2.4.3.5. Pathological Correlates

Tissue specimens will be collected by pathology after which they will be formalin-fixed and paraffin-embedded according to standard procedures.

Specifically, for the LN specimens we will investigate the following:

To determine biological characteristics associated with fluorescence intensity measurements, formalin-fixed paraffin-embedded blocks from the collected specimens will be obtained from pathology after routine analysis and imaged on the Pearl and Odyssey as previously described in preclinical models (72,73). This will allow high-resolution evaluation of the location of the fluorescence signal in the tissue. Subsequently 5 micron sections will be cut for histological analysis of: 1) Size of the epithelial tumor compartment in percent of total; 2) Tumor characteristics (ie, size, proliferation); and 3) EGFR. Methods have been previously described by us using *in vivo* models (74–78).

We will then determine if these characteristics are associated with fluorescence (yes/no) from the Pearl and Odyssey imaging systems. We will use the two-sided Fisher's exact test to determine the level of association between tumor characteristics (ie, size, proliferation) and EGFR status and fluorescence (yes/no). Likewise, we will test the association between the size of the epithelial tumor compartment and fluorescence (yes/no) with the two-sided Wilcoxon rank sum test.

To determine where panitumumab-IRDye800 localizes in the fluorescent LNs, 5 micron sections will be cut and undergo immunohistochemistry for localization of various immune cells, including B and T-cells, macrophages and dendritic cells. Immunohistochemistry findings will then be correlated with fluorescence intensities measured on the Pearl and Odyssey imaging systems. We expect that panitumumab-IRDye800 both specifically and non-specifically occurs in the LNs. Specific uptake in the LNs will occur if metastasis are present in the nodes. Non-specific uptake of panitumumab-IRDye800 in the LNs can occur by a mechanism similar to the principle of SNs mapping, ie, due to accumulation of tracer at the injection site, overflow from the tumor to the LNs will occur where this tracer will get trapped in immune cells (79).

The two-sided Fisher's exact test will be used to determine the level of association between each of these characteristics and panitumumab-IRDye800 fluorescence (yes/no).

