12. STATISTICAL CONSIDERATIONS

12.1 Statistical Design

12.1.1. Primary Objective and Endpoint

The **primary objective** of the study is to determine if near-infrared fluorescence imaging of panitumumab-IRDye800 can identify metastatic disease in regional neck LNs of subjects with HNSCC.

The **primary endpoint** is: The number and location of panitumumab-IRDye800 positive LNs that are also tumor-positive at (histo-)pathology.

To **answer the primary objective**, we will calculate the sensitivity and specificity of the intraoperative findings on whether the LN is fluorescent (ie, presence of panitumumab-IRDye800) to the histopathological (gold standard) status of the LNs.

We will use the matched pair Durkalski's test (80), accounting for the cluster-correlation within subject, for all sensitivity and specificity comparisons (primary and secondary) using the clust.bin.pair package (81) in the R statistical software (84). Significance for both primary and secondary analyses will be assessed at the 0.05 level and to assess uncertainty, 95% confidence intervals will be provided for all estimates.

Descriptive statistics for continuous characteristics (eg, size of the tumor compartment) will include mean, standard deviation, median, interquartile range, minimum, and maximum values. Frequencies and percentages will be used to summarize categorical data. Graphical tools such as heat maps, histograms, and boxplots will be used to assess distributional properties of continuous variables.

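### Tumor size and proliferation are tested against fluorescence with Fisher's exact test and no stated categories, which discards their ordering; the Wilcoxon test used in the next sentence would keep it

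*Combined protocol and SAP*

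**What the plan says.** Section 2.4.3.5 (Pathological Correlates) lists three things to be read from the nodal sections. The first is epithelial compartment size as a percentage of the total. The others are "Tumor characteristics (ie, size, proliferation); and 3) EGFR". Two tests against fluorescence follow:

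- Size, proliferation and EGFR get a two-sided Fisher's "exact test to determine the level of association between tumor characteristics (ie, size, proliferation"), with EGFR status named alongside them and fluorescence yes/no as the outcome.
- Compartment size gets a rank test: "Likewise, we will test the association between the size of the epithelial tumor compartment and fluorescence (yes/no) with the two-sided Wilcoxon rank sum test".

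No unit, scale, grade or cut-point is given for size or proliferation. Section 2.4.3.6 refers the statistical analysis to Section 12, which does not return to these tests. The significance level there is stated only for the main analyses: "Significance for both primary and secondary analyses will be assessed at the 0.05 level".

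**The concern.** Two size variables from the same tissue are compared with the same yes/no outcome by different kinds of test, and no reason is given. Fisher's test treats its categories as unordered labels. It asks whether the fluorescent share differs somewhere, not whether it rises with size or proliferation. It also needs groups, and none are defined.

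At stake is how well the study can show whether small or slowly proliferating deposits are the ones that fail to fluoresce. The background section gives detection of (micro-)metastasis as an aim, and few tumor-positive nodes are expected, so avoidable loss of information matters.

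**Working it through.** **Inputs.** Section 12.1.3 expects 30 to 60 tumor-positive nodes out of 600, in 6 to 8 of 20 subjects. Only tumor-positive nodes have a tumor size or proliferation to measure. The plan gives no effect size, power or fluorescent share for these tests, so there is no figure of its own to reproduce. The following are assumed: two-sided 0.05, a normal shift of 1 SD between fluorescent and non-fluorescent nodes, independent nodes, and about 50% to 75% of tumor-positive nodes fluorescent (0.75 is the lower sensitivity in Section 12.1.3).

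**Step 1: ungrouped values, no ties.** With n nodes, k of them non-fluorescent, and every value distinct, each row of the n x 2 table has total 1. Every table with those margins has probability 1/C(n,k). All tables are equally likely, so the p-value sums over all of them: p = C(n,k) x 1/C(n,k) = 1. For n = 12 and k = 4, that is 495 x 1/495 = 1. The data play no part. Ties, for instance from rounding, break this result.

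**Step 2: median split, large samples.** Under a normal shift, efficiency relative to the t-test is 2/π = 0.637 for a median split and 3/π = 0.955 for Wilcoxon. The ratio is 0.637/0.955 = 0.667, a loss of one third of the effective sample size.

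**Step 3: power at the expected numbers.** Simulation under the assumptions above:

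| Fluorescent / not | Wilcoxon | Fisher, median split | Loss (points) |
|---|---|---|---|
| 22 / 8 | 60% | 41% | 19 |
| 22 / 23 | 89% | 65% (median node counted low) | 24 |
| 33 / 12 | 79% | 49% (median node low) or 71% (high) | 30 or 8 |
| 34 / 11 | 77% | 58% (median node low) or 52% (high) | 19 or 25 |
| 30 / 30 | 96% | 76% | 20 |
| 45 / 15 | 90% | 56% | 34 |

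The loss runs from 8 to 34 points. With an odd number of nodes it depends on which half receives the median node.

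**Step 4: why the loss is uneven.** Fisher's test on small groups moves in coarse steps. Take 30 nodes split 15/15 at the median:

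- With 8 non-fluorescent nodes, having 7 of them in the lower half gives p = 2 x [C(15,7) x 15 + C(15,8)]/C(30,8) = 2 x (96,525 + 6,435)/5,852,925 = 0.035.
- With 7 non-fluorescent nodes, having 6 in the lower half gives p = 2 x [C(15,6) x 15 + C(15,7)]/C(30,7) = 2 x (75,075 + 6,435)/2,035,800 = 0.080, so all 7 must fall there.
- With 3 non-fluorescent nodes (90% fluorescent, outside the range above), the smallest possible p is 2 x C(15,3)/C(30,3) = 2 x 455/4,060 = 0.22. Significance is then out of reach.

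**Step 5: three groups.** Tertiles do not remove the loss. With 30/30 and a shift of 0.74 SD, chosen for a nominal Wilcoxon power of 80%, simulated power is 78% for Wilcoxon and about 61% for Fisher on tertiles.

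**The case against.** The best defense is that the two tests reflect a deliberate division. Compartment size is explicitly a percentage and gets a rank test. Size and proliferation sit beside EGFR status and may be scored in groups, by methods referred to cited papers. This stands in part: the protocol does not give the scale, so calling these variables continuous is an inference. It does not rescue the choice of test, because grades of size or proliferation would still be ordered. With two groups the tests differ little, but the groups would then need to be stated.

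Several stronger readings are tempting, and the documents do not support them:

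- **The planned test must return p = 1.** That needs ungrouped values with no ties. Nothing in the protocol says Fisher's test will be run that way, and naming it suggests that groups are intended.
- **A third or more of the power is lost.** One third is the asymptotic efficiency loss of a median split. In Step 3 the relative power loss ranges from 10% (8/79) to 38% (34/90).
- **Section 12.1.1 contradicts this section.** Its example, "Descriptive statistics for continuous characteristics (eg, size of the tumor compartment"), matches the item that already gets the Wilcoxon test, not the separate tumor size at issue.
- **Cut-points will be picked after seeing the data.** The plan leaves this open but does not say so.

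It is also fair to say that missed metastatic nodes are addressed by the primary sensitivity analysis. This correlate uses laboratory imaging of processed tissue, and relative tumor burden is already covered by the compartment-size test.

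**Conclusion.** The point holds as a minor one. A test that ignores order is assigned, without categories, to two variables that are naturally measured or ordered, while a better test for the same question stands in the next sentence. The cost is about one third of the asymptotic efficiency for a median split under a normal shift, and about 8 to 34 percentage points of power in the splits examined.

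The power figures rest on the assumed 1 SD shift, normality, fluorescent share and independence of nodes. Clustering within subjects would change them for both tests. A reader might infer that the trial's conclusions on sensitivity and specificity are at risk. They are not: Section 2.4.1 calls the study exploratory, and neither the primary nor the secondary analysis uses these tests.

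**What to change.** In Section 2.4.3.5, test tumor size and proliferation against fluorescence with the two-sided Wilcoxon rank sum test already used there, whether they are recorded as measurements or as ordered grades. Keep Fisher's exact test for binary or unordered items such as EGFR positive/negative. State the scale of each variable, and if any is to be grouped, fix the cut-points in advance.

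Allow for nodes sharing a subject where feasible, for example with a clustered rank sum test. With only 6 to 8 subjects expected to have metastatic nodes, such a test is approximate and should be reported as exploratory. Fisher's test has the same dependence problem for EGFR.

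The cost is a sentence or two of text and no new data. The one real burden is the clustered version, which has few clusters to work with.

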Step 1) *In situ* imaging: After having opened the skin and exposure of the neck LNs, *in situ* fluorescence imaging will be performed to evaluate the fluorescence-based visibility of the LNs. For each fluorescent LN, the respective location will be documented (level Ia, Ib, IIa, IIb, III, IV or V) after which it will be harvested by the surgeon. This process will be repeated until no fluorescent LNs are seen *in situ*. Hereafter, the standard of care completion neck dissection will be performed.

Step 2) *Ex vivo* imaging: The neck dissection specimen will be evaluated for the presence of fluorescent LNs using both a closed-field imaging device and an open-field device. All additional fluorescent LNs will be identified, documented and collected separately; we acknowledge that the penetration depth of the fluorescence signal is limited and therefore deeper located LNs might not be detectable *in situ* (under step 1), but after having taken out the specimen and having “flipped” the specimen this might be possible.

Step 3) Wound bed imaging: This will be conducted for any remaining fluorescence (ie, any remaining fluorescent LNs). Areas in the wound bed determined fluorescence-positive will be surgically re-evaluated, and, if deemed necessary by the surgeon, removed.

Step 4) Pathological imaging: All excised nodal specimens will be imaged once more in the closed-field device to confirm that all fluorescent LNs have been removed from the neck dissection specimen. If not, the number and location of remainder fluorescent LNs will be documented after which they will be harvested; we will use the image taken under step 2 for reference as such to make sure that we did not create any confounding factor due to tissue

preparation to harvest nodes at step 2. Hereafter all excised nodal specimens will be sent for (histo-)pathology. After the tissue has been processed and evaluated by the pathologist, fluorescence imaging-based findings will be compared to gold-standard histological-assessment performed by the pathologist (including a hematoxylin and eosin (H&E) staining) to determine the correlation between fluorescence and the presence/absence of tumor tissue in the LN(s).

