12.1.3. Sample Size Justification and Power Considerations

We expect to enroll 10 T1/T2 node-negative subjects and 10 subjects with T1-4 and LN metastasis. Based on the data on LN collection from our current IRB-35064 study, we expect that 50% of subjects will undergo a bilateral neck dissection, meaning we would have a total of 30 necks. Assuming an average of 20 LN harvested per neck we would have a total of 600 LNs. Based on previous findings from our IRB-35064 study, we expect approximately 30-40% of subjects (6 to 8 of 20) will have metastatic LNs with an overall prevalence of 5 to 10% of the total number of harvested LNs (30 to 60 of 600) being tumor-positive.

Since this is a Phase 2 study, power considerations are limited but even so, we have excellent power to detect differences in specificity. Although we will use Durkalski's test to compare sensitivities and specificities, we estimated power by first determining the effective sample size (ESS), adjusting for the correlation of LNs within person, and then estimated power using McNemar's test on this ESS. We assumed an intra-class correlation of 0.005, yielding an effective sample size of 524 LNs. With an effective sample size of 524, a prevalence of 7.5%, a significance level of 0.05, and a 0.25 proportion of discordant pairs, we have greater than 99% power to detect a 0.1 difference in specificities, assuming the lower specificity is 0.8. Similarly, we have greater than 78% power to detect a 0.2 difference in sensitivity with the one-sided McNemar test. This assumes the proportion of discordant pairs is 0.25 and the lower sensitivity is 0.75.

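### Immune-cell staining is described for fluorescent nodes, but its only named test is Fisher's exact test against fluorescence yes/no, which is uninformative at node level

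*Combined protocol and SAP*

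**What the plan says.** Section 2.4.3.5 (Pathological Correlates) describes two pieces of laboratory work.

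The first covers tumor characteristics and EGFR. Its material is broad: "formalin-fixed paraffin-embedded blocks from the collected specimens will be obtained from pathology after routine analysis and imaged on the Pearl and Odyssey". Fisher's exact test and a Wilcoxon rank sum test are assigned to it, with yes/no taken from the Pearl and Odyssey systems.

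The second covers B cells, T cells, macrophages and dendritic cells. It opens: "To determine where panitumumab-IRDye800 localizes in the fluorescent LNs, 5 micron sections will be cut and undergo immunohistochemistry for localization of various immune cells". Two analyses follow. One is a correlation: "Immunohistochemistry findings will then be correlated with fluorescence intensities measured on the Pearl and Odyssey imaging systems". No method is named for it. The other closes the section: "The two-sided Fisher's exact test will be used to determine the level of association between each of these characteristics and panitumumab-IRDye800 fluorescence (yes/no").

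Section 2.4.3.6 refers the reader to Section 12 for statistics. Section 12 deals with sensitivity, specificity, descriptive summaries and power, and says nothing about the immune-cell work.

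**The concern.** Nodes enter the second piece of work because they fluoresce, and the named test then asks whether their immune-cell content is associated with fluorescing. Selecting the sample on the variable to be tested leaves nothing to compare.

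The question behind the test matters for reading the trial. The section expects some uptake to be non-specific, through trapping of the agent in immune cells. That is the plan's own explanation for nodes that fluoresce without tumor, which are the false positives that lower specificity in the primary analysis. Section 2.1 reports a positive predictive value of 50.7% for the earlier cetuximab-based agent, so 100 − 50.7 = 49.3% of its fluorescent nodes were tumor-negative. A p-value of 1 from an empty comparison could be misread as evidence that immune cells play no part.

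**Working it through.** The plan states no sample size, power or expected result for this test, so there is no figure to reproduce. The check is whether the test can carry information under each reading of the text.

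**Reading A: the node is the unit, and one fluorescence reading both selects and classifies it.** Let n1 be the number of fluorescent nodes, n0 the number of non-fluorescent nodes, N = n1 + n0, and K the number of marker-positive nodes. Fisher's test uses

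P(k) = C(K, k) × C(N − K, n1 − k) / C(N, n1).

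With n0 = 0 we have N = n1, so k = K is the only possible table, P = 1 and p = 1. Direct evaluation of every table with n1 from 1 to 120 and k from 0 to n1 returned p = 1.0 each time.

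**How far this depends on the empty margin.** Inputs for an illustration:
- 600 nodes (Section 12.1.3: "Assuming an average of 20 LN harvested per neck we would have a total of 600 LNs"), taken at face value.
- Prevalence of tumor-positive nodes 5 to 10%, planning value 7.5% (Section 12.1.3).
- Sensitivity 97.2% and specificity 92.7% (Section 2.1). These belong to cetuximab-IRDye800 and are assumed to carry over.

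Fluorescent nodes = 0.972 × positives + (1 − 0.927) × negatives.

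| Prevalence | Positives | Fluorescent, tumor-positive | Fluorescent, tumor-negative | All fluorescent | Non-fluorescent |
|---|---|---|---|---|---|
| 5% | 30 | 29.2 | 41.6 | 70.8 | 529.2 |
| 7.5% | 45 | 43.7 | 40.5 | 84.3 | 515.7 |
| 10% | 60 | 58.3 | 39.4 | 97.7 | 502.3 |

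Take 84 fluorescent nodes. With one non-fluorescent node added, the smallest attainable two-sided p is 1/85 = 0.012. With two added, it is 1/C(86, 2) = 1/3655 = 0.00027. So p = 1 is forced only while the margin is completely empty.

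With a real comparator the contrast becomes useful. Suppose, as an assumption, that a marker is present in 67 of 84 fluorescent nodes (80%) and 42 of 84 non-fluorescent nodes (50%). Fisher's p is then 0.00009, ignoring clustering.

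**Reading B: regions or sections within a node are the unit.** Dark and bright areas of one node can then populate both rows. However, several units come from one node and several nodes from one subject, and Fisher's test treats all of them as independent. The plan corrects for this elsewhere. Section 12.1.1 uses a cluster-adjusted test. Section 12.1.3 deflates 600 nodes at 600/20 = 30 per subject to 600 / (1 + 29 × 0.005) = 524. The documents give no correlation for regions within a node, so the size of the error under this reading cannot be computed.

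**Reading C: nodes are selected by the surgical reading and classified by Pearl/Odyssey.** Some nodes could then score no. The comparison would be between nodes on which the devices agree and nodes on which they disagree, which is not the question asked.

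**The case against.** The strongest reply is that the empty margin is partly supplied by the reader. The section never says that fluorescent nodes alone will be stained; it states an aim and is silent about other nodes. Non-fluorescent tissue will exist, because Section 2.4.3.3 says: "Hereafter all excised nodal specimens will be sent for (histo-)pathology". The aim concerns location within a node, and of the laboratory imaging the section says: "This will allow high-resolution evaluation of the location of the fluorescence signal in the tissue". That fits scoring by region at least as well as scoring by node. The same section also plans the intensity correlation, which works when every node is fluorescent.

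Much of this stands. A reader might infer that the plan forbids staining non-fluorescent nodes, that the test can return only p = 1 with zero power at any sample size, or that the whole immune-cell analysis will report no association whatever the biology. The documents support none of these. The first is an inference from silence. The second needs Reading A, and neither the unit nor the fluorescence reading is stated for this test. The third overlooks the intensity correlation.

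The reply does not rescue the test as written. No comparator is named here or in Section 12, while the preceding analysis draws on collected specimens in general, so fluorescent nodes are the plain reading of the sample. Each alternative brings its own defect: unmodeled clustering under Reading B, device disagreement under Reading C. The intensity correlation has no stated method.

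**Conclusion.** The concern holds in a limited form. The only test named for the immune-cell findings is uninformative if the node is the unit and the selecting reading also defines yes/no. It ignores clustering within node and subject if regions or sections are the unit. The intensity correlation is sound in principle but unspecified.

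The conclusion rests on taking fluorescent nodes to be the stained sample, since no other is named. The node counts above are illustrative, and the conclusion does not depend on them.

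The consequence is small for the trial as a whole. This is an exploratory tissue correlate outside the primary and secondary objectives, and no endpoint changes. It should still be corrected, because it is the plan's only analysis of the immune-cell mechanism it proposes for non-specific uptake.

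**What to change.** In Section 2.4.3.5, for the immune-cell characteristics:

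- Replace the Fisher yes/no test with an analysis of immune-cell findings against continuous Pearl/Odyssey intensity that accounts for clustering within subject, for example a mixed model with a subject effect. If there are several regions or sections per node, add a node effect.
- Report it separately for tumor-negative and tumor-positive nodes. Section 12.1.3 expects metastatic nodes in only 6 to 8 of 20 subjects, so the tumor-positive results should be presented as estimates with intervals.
- Keep a yes/no contrast only if non-fluorescent nodes are included in the stained sample, preferably from the same subjects and with allowance for clustering.
- State the unit of analysis (node, section or region) and which fluorescence reading is used.

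The first, second and fourth changes cost wording and some analysis time; the intensity measurements are already planned. The third needs extra slides from nodes that already go to pathology, and only if the yes/no contrast is wanted.
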